RC can take a screen shot of the patient's remaining pills-per bottle. The RC will save the screen shot/photograph to the study project folder within the secure GIM server only using the patient's studyid to identify the photograph. No PHI will be captured in the photograph. If the participant does not have video capabilities, the RC will proceed to explain how the patient can count their pills and relay the number to the RC. This script is outlined in the interview script. For patients consented before May 19, 2020 that complete a phone 6 month, a brief script will be read informing patients of the change in the consent in regards to the pill count. The RC will ask the participant to provide verbal consent to allow the study team to take a screen shot/photograph of the patient's pills during a video call in order for the RC to count the pills after the interview. The patient will be notified that no PHI will be captured in the photograph.

**Medication reconciliation.** Chart reviews will determine whether any discrepancies are present between patient self-report and the chart medication list. Nature of the discrepancy (omission vs. commission) will be recorded.

**Clinical Outcomes.** Systolic/diastolic blood pressure will be collected on all patients during the baseline and 6 month interview. Low-density lipoprotein cholesterol (LDL) will be obtained from patients' electronic health records. Chart review of hemoglobin A1c (hbA1c) will be reviewed for all diabetic patients. Differences will be measured between the last clinical measurement prior to baseline assessment and the last measured value during the study period (closest to 6 month assessment).

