## 11.0 Data and Specimen Management

### 11.1 Analysis Plan.

#### Aim 1.

The proposed trial uses patient 1:2:2:2 randomization with random block size to achieve group comparability and balance. Stratified by clinic, each participant will be randomized to one of the four arms. The four arms are the result of a 2x2 factorial design, where SMS text reminder and portal are the two-level factors with all four arms receiving the EHR tools. We conservatively anticipate at least 80% retention for follow-up at six months. This will result in 1505 participants recruited to the study with an anticipated minimum of 1204 (172 participants in EHR arm and 344 per the other arms) available after six months, contributing to primary data analysis. Due to an NIA administrative hold, the interventions were not implemented as planned. Hence it was determined that the primary analysis would be “per-protocol” rather than intent-to-treat to assess the effect of the interventions under optimal conditions. Participants who received the initial 6 weeks of SMS messaging continuously will be considered as receiving the SMS intervention, and participants who logged on to the patient portal and completed at least one survey will be considered as receiving the patient portal.

To ensure adequate balance across treatment arms, baseline outcomes and potential confounders including socio-demographic characteristics, comorbidities, regimen complexity (i.e. # of medications, total pills taken daily), health literacy level, and language will be examined. Variables found to have clinically meaningful differences across treatment groups will be entered as covariates in the generalized linear mixed models (GLMMs) used for formal analyses as described below.

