Prescription medication adherence at 6 months is the primary outcome of interest for Aim 1, with treatment knowledge regimen consolidation, and clinical outcomes being relevant to hypotheses of secondary interest. We will use generalized linear mixed-effects models (GLMMs) to test for the effects of SMS text reminder and Portal, specifying the proper link functions based on the distribution of the outcome variable. Analyses will be performed using PROC GENMOD in SAS (v.9.4). SMS text reminder and Portal (both binary) and an interaction term for SMS and Portal are the three variables included in the model to denote the intervention groups and the enhanced usual care group (H1-6). Since adherence will be assessed for each medication, 2-level GLMM will be used with medications nested in participants. We will test for differences in the outcomes between each of the groups and the enhanced usual care arm to determine benefits of SMS texting or portal use, or both by constructing contrasts.

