Exploratory Analyses. In addition to the primary per-protocol analysis, we will investigate if there is a "dose response" of either intervention. Specifically, we will look at the total weeks participating in SMS text messages and the total number of portal surveys completed. Additionally, we will repeat all GLMM analyses described for Aim 1 to explore whether differences in interventions vary by relevant covariates representing patient and regimen characteristics known to impact outcomes, specifically adherence. Interaction terms will be included in models accordingly. Statistical significance for a tested interaction ( $p < 0.05$ ) will indicate that intervention groups differ in outcomes by the studied variable (i.e. age, literacy level, regimen complexity, drug class, language, activation, comfort with texting or portal, etc.). As adherence has its many measurement challenges, experts recommend triangulating with multiple measures. We will fully investigate and compare results across each adherence measure (24-hour recall, pill count, PDC) and create a general estimate of adherence via single factor score using maximum likelihood estimation. Exploratory analyses will examine HbA1c and blood pressure from baseline to 6 months, although power may be limited.

**COVID-19 Survey:** By extending each of these studies (LitCog (STU00026255), REMinD (STU00203777), COPD Multimorbidity (STU00201640), UMS Portal (STU00201639), and TAKE IT (STU00204465)) to capture an additional patient-reported outcome related to one's knowledge, attitudes and behaviors related to COVID-19, we can link participants' responses to this longitudinal survey to a minimum data set of participant characteristics that include demographic, socioeconomic, cognitive (including health literacy) and health behavioral characteristics. We will then be able to investigate determinants of COVID-19 knowledge, attitudes and behaviors without duplicating data collection efforts for these variables.

[name] will be analyzing data from the Wave 1 health literacy items.

RCs will conduct interviews by telephone using REDCap survey software. [name] (analyst) will oversee database structure & quality assurance. Participants will complete 5 phone interviews with RCs.

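### Baseline adjustment of LDL, HbA1c and possibly blood pressure depends on an undefined imbalance check; where the check finds nothing, the plan leaves unadjusted change, which is less precise

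*Combined protocol and SAP*

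**What the plan says.** Section 8.2 (Clinical Outcomes) states: "Differences will be measured between the last clinical measurement prior to baseline assessment and the last measured value during the study period", with the later value being the one nearest the 6-month assessment. LDL and HbA1c come from the health record. Blood pressure is different: "Systolic/diastolic blood pressure will be collected on all patients during the baseline and 6 month interview".

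Section 11.1 (Aim 1) sets the default model: "SMS text reminder and Portal (both binary) and an interaction term for SMS and Portal are the three variables included in the model". No baseline-outcome term is among them.

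The same section has a conditional rule. It begins "To ensure adequate balance across treatment arms, baseline outcomes and potential confounders including socio-demographic characteristics" and says that these and other listed factors will be examined. It continues: "Variables found to have clinically meaningful differences across treatment groups will be entered as covariates in the generalized linear mixed models (GLMMs". It does not say how large a difference counts as clinically meaningful for any of these measures.

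On rank, section 11.1 describes "clinical outcomes being relevant to hypotheses of secondary interest". Its Exploratory Analyses paragraph adds: "Exploratory analyses will examine HbA1c and blood pressure from baseline to 6 months, although power may be limited". LDL is not named there. The primary analysis is per-protocol, with groups defined by receipt; for SMS, "Participants who received the initial 6 weeks of SMS messaging continuously will be considered as receiving the SMS intervention".

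**The concern.** The precision gained by adjusting for baseline comes from the correlation between baseline and follow-up. It does not depend on the groups being imbalanced. A rule triggered by imbalance therefore omits the covariate in exactly the situation where the groups look alike, and the precision loss of a raw change score then stands in full. The plan itself concedes limited power for HbA1c and blood pressure, so avoidable variance matters.

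Because no threshold is set, the decision to adjust is made after the baseline data are seen, separately for each outcome. Two analysts could follow the plan and report different estimates. Gaps judged too small to matter clinically go uncorrected, although they still shift a change-score comparison.

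Groups defined by continuous text receipt or portal use may also differ at baseline for reasons other than chance. That is a further reason not to leave the model to judgement.

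**Working it through.** **The plan's own figure.** The documents give no power, SD or correlation for LDL, HbA1c or blood pressure. The only power statement (section 11.2) concerns 24-hour-recall adherence: 69% versus 81%, 172 versus 344 evaluable, alpha 2.5%. At two-sided 2.5% this reproduces as 78.1% against the stated 80%. The sample size reproduces exactly: 1204/0.80 = 1505. Neither figure bears on the clinical outcomes. Only the arm sizes are used below.

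**Step 1: variance.** Let s be the SD, equal at both times, and r the baseline to follow-up correlation. Per patient:

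- Change score: 2(1−r)s²
- Follow-up adjusted for baseline: (1−r²)s²
- Ratio: 2(1−r)/[(1−r)(1+r)] = 2/(1+r)

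**Step 2: detectable difference.** For 172 versus 344, two-sided 2.5% and 80% power, in units of s: (2.241 + 0.842) × √(1/172 + 1/344) × √V = 3.083 × 0.0934 × √V = 0.288√V, where V is the variance from step 1 with s = 1.

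| r (assumed) | V, change | V, adjusted | Ratio | Variance saved by adjusting | Detectable difference, change vs adjusted |
|---|---|---|---|---|---|
| 0.4 | 1.20 | 0.84 | 1.43 | 30% | 0.315 vs 0.264 |
| 0.5 | 1.00 | 0.75 | 1.33 | 25% | 0.288 vs 0.249 |
| 0.6 | 0.80 | 0.64 | 1.25 | 20% | 0.258 vs 0.230 |
| 0.7 | 0.60 | 0.51 | 1.18 | 15% | 0.223 vs 0.206 |
| 0.8 | 0.40 | 0.36 | 1.11 | 10% | 0.182 vs 0.173 |
| 0.9 | 0.20 | 0.19 | 1.05 | 5% | 0.129 vs 0.125 |

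The detectable differences are illustrative. HbA1c is reviewed only for diabetic patients (section 8.2), and phone interviews yield no in-person blood pressure (section 9.12). Real numbers will be smaller and detectable differences larger. The ratio column does not depend on n.

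**Step 3: uncorrected gaps.** Under randomisation, a chance baseline gap D shifts the unadjusted change comparison by −(1−r)D. In a 172 versus 344 comparison, D has an SD of √(1/172 + 1/344) = 0.093 s. The typical shift is 0.5 × 0.093 = 0.047 s at r = 0.5 and 0.2 × 0.093 = 0.019 s at r = 0.8, or roughly 0.02 to 0.05 s.

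**Step 4: what happens when the trigger fires.** In a linear model, regressing change on baseline plus treatment terms differs from regressing follow-up on the same terms only by adding 1 to the baseline slope. The treatment coefficients are identical. So where the conditional rule brings the baseline value in, the plan already gives the adjusted contrast.

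**The case against.** A reader might infer that the plan analyses raw change and never adjusts for baseline, so that baseline differences become apparent effects. The documents do not support that. Section 8.2 is an endpoint definition and names no model. The Aim 1 rule covers baseline outcomes and enters them when groups differ meaningfully, which by step 4 gives the adjusted contrast. The case of a large imbalance is therefore mostly covered.

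A reader might also infer that any group with a higher baseline will falsely appear to improve. Under randomisation, raw change is unbiased on average, and the step 3 shift is conditional on the observed gap. In groups defined by receipt the formula need not hold: if the groups have stable, different true means, change is not distorted by regression to the mean, and adjusting for baseline can itself introduce bias.

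Three more limits stand. It is unclear whether the difference rule governs blood pressure measured at interview or only the chart-derived LDL and HbA1c. The size depends on an r that the documents do not give, and the gain is small if r is 0.8 or 0.9. Finally, H1 to H4 all concern adherence, so none depends on these outcomes.

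None of this answers the narrower point. A trigger based on imbalance does nothing for precision when groups look balanced, and a trigger without a threshold is not a prespecified analysis.

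**Conclusion.** The point holds as one of precision and prespecification. Adjustment for the baseline clinical value is neither absent from the plan nor fixed by it. When the check does not lead to adjustment, unadjusted change has 1.05 to 1.43 times the variance of the adjusted estimate for assumed r from 0.9 down to 0.4, and chance gaps of typical size move the comparison by about 0.02 to 0.05 SD (r = 0.8 to 0.5). The calculation assumes equal SDs at the two times and ignores the small cost of estimating the slope. The outcomes affected appear under Primary Endpoints in section 8.2, but section 11.1 treats them as secondary or exploratory, so the trial's main conclusion is not at risk. The change is still worth making because it costs almost nothing.

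**What to change.** In section 11.1, state that each clinical outcome will be analysed in every case by a linear model for the follow-up value (or, equivalently, the change), with the same-source baseline value as a prespecified covariate plus SMS, Portal and their interaction. Report the adjusted difference. For these outcomes' own baseline values, this replaces the imbalance trigger.

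Name the baseline measurement for each outcome and reconcile the sections: section 8.2 uses the last clinical value before the baseline assessment, section 9.12 uses the HbA1c closest to the interview, and blood pressure is measured at the interview. Say whether the difference rule in section 8.2 applies to blood pressure.

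Add a sentence saying that baseline adjustment does not make groups defined by receipt comparable, so selection into the per-protocol groups remains a separate limitation.

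The cost is SAP wording only. The baseline value is already needed to compute the change, so no new data are required and no further patients are lost.

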### 3.0 Inclusion and Exclusion Criteria

3.1 **Methods of screening for eligibility.** Patients will be screened for eligibility by phone after they have had a regularly scheduled doctor appointment. The screener document details the series of questions that will be asked.

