**Hypertensive Emergency Screening Questions:**

Are you currently experiencing...

- Severe pain in the chest and/or upper back?
- Nausea or vomiting?
- New vision changes?
- Severe trouble breathing?
- A headache? (Must say yes to both sub-questions to count as a yes)

- Is it different from prior headaches?
- Is it severe?

The RC will then instruct the patients based on the following for Erie patients:

- For interviews done at an Erie site, and patient has a systolic >180 or diastolic >110: Patient should be transferred in real time to the on-site nurse for a full assessment and provider consultation regardless of responses to screening questions. The RC will provide the patient with their blood pressure values on a piece of paper.
- For interviews done at Northwestern, and patient has a systolic >180 or diastolic >110:
  - Patient should be advised to go to the Northwestern Emergency Department regardless of responses to screening questions before leaving the interview. The RC will provide the patient with their blood pressure values on a piece of paper.
  - The RC should notify Erie Family Health Centers of the patient's blood pressure screening and that the patient was advised to go to the Emergency Department
    - The RC should call Erie directly and follow the phone tree to speak with a Patient Access Representative, [contact]
  - Erie Staff will notify the patient's Primary Care Provider

The RC will then instruct the patients based on the following for Northwestern patients:

- If yes to any screening questions above, patient should either call their PCP's office from the interview room to speak to a healthcare provider for advice, or proceed to the ER.
- If no to all screening questions above, patient should be instructed to call their primary care doctor.

For diabetic patients, a chart review or EDW pull will be done to examine Hemoglobin A1c (hbA1c) levels at their regularly scheduled primary care appointments closest to baseline and 6 month interviews. This is to decrease the burden on the participant – alternatives include taking a blood sample at our interview or asking participants to go to Quest Diagnostics. We felt that was excessive and unnecessary, so will use the EHR data provided by Erie or the EDW report for Northwestern patients.

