  - Primary language
  - Date of last primary doctor appointment at Erie
  - All drugs prescribed (name, dose, form, GPI, instruction, date prescribed, number of refills, pharmacy, quantity)
- NU will send Alliance/Erie Family Health Center Study IDs and baseline interview dates, linked by patient ID
- Alliance will send the following information to Northwestern for consented patients:
  - Study ID
  - All values 6 months prior to baseline & 12 months post
    - Blood pressure
    - HbA1c
    - Cholesterol levels
  - Information on all prescribed medicines baseline to 12 months post (name, dose, form, GPI, instruction, date prescribed, number of refills, pharmacy, quantity)
  - Current at baseline and 12 months post
    - Chronic conditions
    - COVID-19 diagnosis and/or results of antibody test
  - All clinic visits/appointments 6 months prior to baseline and 12 months post (date, provider, meds prescribed, visit type)
  - Patient portal survey results, date completed, and possible clinic contact for patients in either of the portal arms
  - Patient portal use 6 months prior to baseline and 36 months post baseline
    - how many times patient logged on to portal
    - what portal was used for
    - when and how often portal was used

For Northwestern patients, the same data that was requested above will be obtained through an additional EDW report, including patient medications, chronic conditions, COVID-19 diagnosis and/or results of antibody test, and healthcare utilization (ED, hospitalization, primary care appointments) as well as hypertension, diabetes and cholesterol clinical values.

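### Follow-up HbA1c and LDL are taken from routine records with no minimum time after baseline and no single selection rule, so an early result can stand as the 6-month outcome

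*Combined protocol and SAP*

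**What the plan says.** Section 8.2 sets the clinical change score. The starting value is fixed by "Differences will be measured between the last clinical measurement prior to baseline assessment", and the follow-up value is "the last measured value during the study period (closest to 6 month assessment". For LDL the source is routine care: "Low-density lipoprotein cholesterol (LDL) will be obtained from patients' electronic health records".

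Section 9.12 states the HbA1c rule a second time, as levels "at their regularly scheduled primary care appointments closest to baseline and 6 month interviews". It records that a study blood sample was considered and rejected: "We felt that was excessive and unnecessary, so will use the EHR data provided by Erie or the EDW report for Northwestern patients". It gives no LDL rule.

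Three other places bear on timing:

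- Section 3.1 ties enrolment to a clinic visit: "Patients will be screened for eligibility by phone after they have had a regularly scheduled doctor appointment". Section 7.1 places the baseline interview after such a visit and gives participation as 6 months.
- Section 9.19 sets the extraction range for blood pressure, HbA1c and cholesterol: "All values 6 months prior to baseline & 12 months post".
- Section 11.1 makes 6-month adherence the primary outcome and clinical outcomes secondary. It lists HbA1c under exploratory analyses and concedes that power may be limited.

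**The concern.** No laboratory sample is timed by the protocol, so the selection rule alone decides which result represents month 6. The rule has no lower limit. A patient whose only result after baseline comes in the first weeks satisfies the wording of 8.2, and that result enters the analysis as the 6-month outcome.

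Such a value says little about the intervention. Under section 11.1, SMS receipt means the initial 6 weeks of messages without a break, and portal receipt means logging on and completing at least one survey. Section 9.15 schedules the first survey request at 2 weeks. A result from day 7 precedes both the first survey request and the end of the SMS run. This holds for LDL as well as HbA1c and needs no biological model.

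Two analysts could also follow the protocol and build different datasets, because *last in the study period* and *closest to 6 months* are not the same rule. At stake is whether the HbA1c and LDL comparisons can be interpreted. A null result could reflect mistimed sampling.

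**Working it through.** **The plan's own figure.** The documents give no SD, effect size or power for HbA1c or LDL. The only design calculation with full inputs is for 24-hour-recall adherence (section 11.2). Retained: 1505 × 0.80 = 1204, or 172 and 3 × 344. For 69% vs 81%, two-sided alpha 2.5%, pooled-variance normal approximation:

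- pooled proportion = (172 × 0.69 + 344 × 0.81)/516 = 0.77
- null SE = √[0.77 × 0.23 × (1/172 + 1/344)] = 0.0393
- alternative SE = √[0.69 × 0.31/172 + 0.81 × 0.19/344] = 0.0411
- power = Φ[(0.12 − 2.241 × 0.0393)/0.0411] = 78.1%, within 2 points of the stated 80%

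Nothing in this depends on laboratory timing.

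**The two rules side by side.** Take the 6-month assessment as day 180 and a patient with results at days 7 and 210.

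- *Last in the study period*, read as 6 months of participation: day 7.
- *Closest to 6 months*, using the 12-month extraction: day 210, since 210 − 180 = 30 and 180 − 7 = 173.

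Under *closest*, day 7 is chosen only if there is no other result until about day 180 + 173 = 353. The early-value problem is therefore mainly one of the *last* reading, or of patients with no other result.

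**How much an early HbA1c captures (assumption).** Suppose HbA1c weights the previous 120 days linearly, most recent days heaviest, and the glucose effect is full from day 0. The fraction captured at day t is f(t) = 1 − (1 − t/120)² for t < 120, and 1 afterwards.

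| Day | 14 | 30 | 60 | 90 |
|---|---|---|---|---|
| Captured | 22% | 44% | 75% | 94% |

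This curve does not apply to LDL.

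**How many values might be early (assumption).** If routine tests occur at random with mean interval m months and the last result within 6 months is used, then among patients with at least one result

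P(last result before month t) = e^(−(6−t)/m) × (1 − e^(−t/m)) / (1 − e^(−6/m)).

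| Mean interval | Within 1 month | Within 2 months | Within 3 months |
|---|---|---|---|
| 3 months | 6% | 15% | 27% |
| 6 months | 11% | 23% | 38% |
| 12 months | 13% | 28% | 44% |

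Averaging f(t) over the same distribution of last-test days, with 30-day months, gives a mean capture of 90%, 85% and 81%. As a harsher bound, if values from the first 2 months carried no effect, the observed effect would be 0.85, 0.77 or 0.72 of the true one (1 minus the within-2-months share).

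**The late end.** Suppose instead that the effect stops at day 180 (assumption). Capture at a later day t is then 1 − f(t − 180): 56% at day 210, 25% at day 240 and 6% at day 270. For a single test uniform over the window:

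- Days 90–210: integral over 90–120 = 29.375, over 120–180 = 60, over 180–210 = 23.125; total 112.5/120 = 94%.
- Days 90–270: 29.375 + 60 + 39.375 = 128.75; 128.75/180 = 72%.

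A late limit matters as much as an early one.

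**The case against.** The strongest reply is that both sections aim at month 6. An early value is used only when nothing later or closer exists, and under 9.12 a result from the enrolment visit belongs to the appointment nearest baseline, not the one nearest 6 months. This stands, and it limits the point to patients with sparse testing or to the *last* reading of 8.2. It does not supply a minimum interval or settle which rule applies.

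The second reply is status. These outcomes appear under the heading Primary Endpoints in 8.2, so a reader might infer that the trial's primary result is at risk. Section 11.1 rules that out.

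Third, a reader might infer a fixed dilution. If every patient had exactly one test, uniform over days 0–180, mean capture would be (80 + 60)/180 = 78%, a loss of 22%. The documents do not support that as the trial's figure. They give no testing frequency, and more frequent testing gives a smaller loss.

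Fourth, a reader might infer that the portal arms, with nurse follow-up, will have fewer early values and so a bias between arms. Sections 9.15 and 9.16 describe review and counselling. Nothing says that this contact leads to laboratory tests. It is a possibility to monitor. If it occurred, the bias need not be towards zero.

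Finally, a window turns early values into missing ones, and that missingness could itself differ by arm. This is a real cost of the fix.

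**Conclusion.** The point holds in a limited form. For HbA1c and LDL, sections 8.2 and 9.12 set no minimum time after baseline and no single selection rule, and the study period is undefined against 6 months of participation and 12 months of extraction. Patients with no later or closer result can contribute a value from days or weeks after baseline, some of it before the per-protocol exposure is complete. If test timing is similar across arms, this pulls the estimated effect towards zero.

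The size is not known. The capture and early-share figures rest on the assumed 120-day linear weighting and random routine testing, neither of which is in the documents, and the capture figures concern HbA1c only. Blood pressure taken at in-person interviews is outside the point. Correcting the rule is worthwhile, but it does not bear on the trial's main conclusion.

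**What to change.** State one rule in 8.2, and repeat or cross-refer to it in 9.12 so that it covers both HbA1c and LDL:

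- Use the value nearest the 6-month assessment within a pre-specified window around it. The window needs a minimum interval after baseline (for example no earlier than day 90) and an upper limit close to the end of the 6-month intervention (for example about day 210). Extending to day 270 would admit values that, if the effect ends with the intervention, capture as little as 6% of it.
- Give a reason for the LDL lower limit, since the HbA1c weighting does not supply one. Any limit after day 42 (6 weeks) falls beyond the SMS run that defines receipt.
- Treat a patient with no in-window value as missing. Report the in-window share and the distribution of test dates by arm.
- Add a sensitivity analysis using any post-baseline value.

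The cost is wording and a small amount of programming. Values to 12 months are already extracted, and no patient contact is added. Some patients whose only result is early lose a follow-up value. Results from day 180 to day 210 replace part of that loss. The remaining missingness could differ by arm, which the reporting and the sensitivity analysis would help to show.
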